10.4 Handling of Multiplicity

No adjustment for multiplicity will be done. In order to claim the study success, both co-primary endpoints need to be statistically significant at significance level 0.05 (two-sided). The co-primary endpoints will be tested prior to the ranked secondary endpoints; and the ranked secondary endpoints are tested for statistical significance only if both the co-primary endpoints meet statistical significance at a two-sided significance level of 0.05.

The statistical test for the ranked secondary endpoints will be carried out in the hierarchical order as specified in Section 10.3. This means that statistical significance for the remaining ranked secondary endpoints is assessed at 0.05 (2-sided) in the above order until the significance level exceeds 0.05. No additional statistically significant treatment differences could be declared after the ranked endpoint fails to achieve statistical significance at a two-sided significance level of 0.05.

10.5 Efficacy Subgroup Analysis

The subgroups listed below will be used in subgroup analyses of the co-primary endpoints.

- Sex (male, female)
- Age (\leq median, $>$ median)
- Race (white, non-white)
- Baseline fecal calprotectin [\leq median, $>$ median]
- Baseline fecal calprotectin [$\leq 250 \mu\text{g/g}$, $> 250 \mu\text{g/g}$]
- Baseline corticosteroid use (YES, NO)
- Baseline immunosuppressants use (YES, NO)
- hs-CRP at Baseline (< 10 and ≥ 10 mg/L)
- hs-CRP at Baseline (\leq median, $>$ median)
- Crohn's disease severity (CDAI ≤ 300 , > 300) at Baseline
- Baseline CDAI (\leq median, $>$ median)
- Baseline SES-CD [\leq median, $>$ median]
- Prior infliximab use (YES, NO)
- Weight (\leq median, $>$ median)
- Baseline albumin (\leq median, $>$ median)
- Disease duration (≤ 3 years, > 3 years)
- Disease duration (\leq median, $>$ median)
- Region (US, ex-US)

11.0 Safety Analysis

11.1 General Considerations

All safety analyses will be performed on the safety analysis set. The safety variable will be summarized by treatment according to the treatment a subject actually received.

11.2 Analysis of Adverse Events

11.2.1 Treatment-Emergent Adverse Events

Treatment-emergent AEs during Induction Study are defined as events that begin or worsen either on or after the first dose of the study drug and within 70 days after the last dose of the study drug for subjects who do not participate in the OLE (Study M14-347) or Maintenance study, or until first dose of maintenance study drug, or until first dose of study drug in the OLE study if the subject who enrolled under Amendment #3 or earlier, is a study completer and is enrolled in the OLE.

The 70-day follow-up phone call will not be required for any subject that initiates commercial adalimumab.

An overview of treatment-emergent AEs, including AEs of special interest such as adverse events leading to death and adverse events leading to premature discontinuation, AEs by Medical Dictionary for Drug Regulatory Activities (MedDRA version 21.0 or later) preferred term and system organ class, AEs by maximum relationship to study drug, and AEs by maximum severity will be summarized by number and percent.

The number and percent of subjects experiencing treatment-emergent adverse events will be summarized for the following adverse event categories.

- Any treatment-emergent adverse event.
- Any treatment-emergent adverse event that was rated as possibly related to study drug by the investigator (Reasonable Possibility).
- Any treatment-emergent severe adverse event.
- Any treatment-emergent serious adverse event.
- Any treatment-emergent adverse event leading to discontinuation of study drug.
- Any treatment-emergent adverse event leading to death.
- Any treatment-emergent adverse event of special interest.
- Any Deaths

Treatment-emergent adverse events will be summarized as follows:

- Grouped by System Organ Class and Preferred Term.
- A by-subject listing will be provided.
- Grouped by System Organ Class, Preferred Term and Severity.
- Grouped by System Organ Class, Preferred Term and Relationship to Study Drug.
- Grouped by System Organ Class and Preferred Term with subject numbers.

In treatment-emergent AE tables, a subject who reports more than one treatment-emergent AE in different system organ classes will be counted only once in the overall total. A subject who reports two or more different preferred terms which are in the same SOC will be counted only once in the SOC total. A subject who reports more than one treatment AE with the same preferred term will be counted only once for that preferred term using the most extreme incident (i.e., most "severe" for the severity tables and most "related" for the relationship tables).

Adverse events will also be summarized by maximum severity. If a subject has an adverse event with unknown severity, then the subject will be counted in the severity category of "unknown," even if the subject has another occurrence of the same adverse event with a severity present. The only exception is if the subject has another occurrence of the same adverse event with the most extreme severity – "Severe." In this case, the subject will be counted under the "Severe" category.

Adverse events will also be summarized by maximum relationship to study, as assessed by the investigator. If a subject has an adverse event with unknown relationship, then the subject will be counted in the relationship category of "unknown," even if the subject has another occurrence of the same adverse event with a relationship present. The only exception is if the subject has another occurrence of the same adverse event with a relationship assessment of "Reasonable Possibility." In this case, the subject will be counted under the "Reasonable Possibility" category, respectively.

Incidence rates per 100 patient years of exposure to study drug will be presented for AE overviews and for AEs by SOC and preferred term where the number of events will be used as the numerator.

All Adverse Events identified to AbbVie from the 70-day follow-up phone call will be collected as source data to be evaluated and reported. Thus, all SAEs and nonserious AEs as defined by AbbVie, reported during the 70-day follow-up phone call must be captured in the clinical database. The end of trial is the last subject contact, i.e., the 70-day follow-up call.

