### 6.1.3 Relationship to Study Drug

The investigator will use the following definitions to assess the relationship of the adverse event to the use of study drug:

Reasonable Possibility	An adverse event where there is evidence to suggest a causal relationship between the study drug and the adverse event.
No Reasonable Possibility	An adverse event where there is no evidence to suggest a causal relationship between the study drug and the adverse event.

For causality assessments, events assessed as having a reasonable possibility of being related to the study drug will be considered "associated." Events assessed as having no reasonable possibility of being related to study drug will be considered "not associated." In addition, when the investigator has not reported a causality or deemed it not assessable, AbbVie will consider the event associated.

If an investigator's opinion of no reasonable possibility of being related to study drug is given, another cause of event must be provided by the investigator for the serious adverse event.

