### **8.1.5 Statistical Analyses of Safety**

Adverse events (AEs), laboratory data and vital signs are the primary safety parameters in this study. All safety comparisons will be performed for both induction and maintenance periods between treatment groups using the safety analysis set.

Treatment-emergent AEs are defined as events that begin or worsen either on or after the first dose of the study drug and within 70 days after the last dose of the study drug for subjects who do not participate in the OLE or until first dose of study drug in the OLE study if the subject is a completer and is enrolled in the OLE.

Treatment-emergent AEs will be summarized separately for: a) Baseline to Week 12; b) Week 12 to Week 56; c) Baseline to Week 56 (overall study duration). An overview of treatment-emergent AEs, including AEs of special interest such as adverse events leading to death and adverse events leading to premature discontinuation (see details in the SAP), AEs by Medical Dictionary for Drug Regulatory Activities (MedDRA version 20.1 or later) preferred term and system organ class, AEs by maximum relationship to study drug, and AEs by maximum severity will be summarized by number and percentage.

Changes in laboratory data will be described using statistical characteristics and compared between treatment groups will be performed using a one-way Analysis of Variance (ANOVA). In addition, shift tables and listings will be provided for abnormal values, whereby the normal range of the analyzing laboratory will be used. Vital signs will be analyzed similarly.

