12.0 Summary of Changes

12.1 Summary of Changes Between the Latest Version of Protocol and the Current SAP

None.

12.2 Summary of Changes Between the Previous Version and the Current Version of the SAP

Under Section 6.0 Analysis Conventions: Only CD related systemic or rectal corticosteroids will be used for censoring purpose, and will have last non-missing value prior to censoring carried forward for non-categorical assessments) from that point forward. This change is made to be consistent with protocol Amendment 6.

In addition, SES-CD scoring rule is updated regarding missing individual variables. The missing SES-CD individual variables at Baseline will be imputed as 0. The post-Baseline missing SES-CD individual variables will be imputed as 0 if there are 8 or fewer missing individual variables. If more than 8 individual variables are missing, the total SES-CD will be missing for that visit. Both changes are based on newly created Analysis Convention for Crohn's Disease and Ulcerative Colitis Clinical Studies. The new imputation rule is also used by current Abbvie IBD registrational trials.

Bristol Stool Form Scale is not a continuous variable. The new variable Bristol Stool Chart score is defined as the number of days the subjects with Type 6 or Type 7 divided by the total number days with non-missing assessments, rounded to two decimal. If a subject achieved reduction from Baseline $\geq 50\%$, this subject will be classified as Bristol Stool Chart Responder. This change is made to be consistent with protocol Amendment 6.

The Week 12 visit window for SES-CD is updated so that no post-baseline Induction data will be discarded. In addition, endoscopy data collected prior to or within 7 days of the fist dose of maintenance study or OLE Study M14-347 will be considered for the Week 12 visit window for SES-CD; thus ensuring endoscopy data collected is not ignored

while also reflecting the efficacy based on the study treatment during the 12 week induction period.

Under Section 10.2, one of the co-primary endpoints, SES-CD ≤ 4 and at least a 2 point reduction versus baseline and no subscore greater than 1 in any individual variable) at Week 12 is replaced by decrease in SES-CD $> 50\%$ from Baseline (or for a Baseline SES-CD of 4, at least a 2 point reduction from Baseline) at Week 12. This change is made to be consistent with protocol Amendment 6.

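### Both SAPs class AEs with missing causality as 'unknown' and omit them from the only drug-related overview row, while Protocol 6.1.3 has the sponsor treat them as associated

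*SAP*

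**What the plan says.** **Protocol.** Section 6.1.3 gives the investigator two ratings, 'Reasonable Possibility' and 'No Reasonable Possibility'. On the first, "events assessed as having a reasonable possibility of being related to the study drug will be considered" associated; the second leads to not associated. For the remaining case it adds that "when the investigator has not reported a causality or deemed it not assessable, AbbVie will consider the event associated". So every event ends in one of two classes. Section 8.1.5 then plans tables in which "AEs by maximum relationship to study drug, and AEs by maximum severity will be summarized by number and percentage". It sets no separate rule for events without a rating.

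**SAPs.** Section 11.2.1 uses the same wording in the Induction and the Maintenance SAP.

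- Basis of the relationship table: "Adverse events will also be summarized by maximum relationship to study, as assessed by the investigator".
- Events without a rating: "If a subject has an adverse event with unknown relationship, then the subject will be counted in the relationship category of" 'unknown'. This holds even if the subject has another occurrence of the event with a rating.
- Exception: "The only exception is if the subject has another occurrence of the same adverse event with a relationship assessment of" 'Reasonable Possibility'.
- The only overview row that depends on causality: "Any treatment-emergent adverse event that was rated as possibly related to study drug by the investigator (Reasonable Possibility").

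**Declared departures.** Under "12.1 Summary of Changes Between the Latest Version of Protocol and the Current SAP", the Induction SAP enters 'None'. The Maintenance SAP lists one corrected efficacy endpoint and four added ones, and nothing on safety.

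**The concern.** The protocol closes the missing-causality case in the cautious direction. The SAPs reopen it with a third category that the protocol does not have, and the overview has no row for that category. The same event can therefore be associated under the protocol and yet not appear in the drug-related figure of the study report.

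Because section 12.1 is silent in both SAPs, a reader of the report would reasonably suppose that the drug-related row follows 6.1.3. No planned output gives the count under the sponsor's own rule. The point has some weight here because Protocol 3.1 describes the induction regimen as higher than any previously studied in Crohn's disease, so its tolerability will be looked at closely.

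**Working it through.** The documents state no figure on this point, so there is none to reproduce. The check compares the two rules case by case.

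**Inputs.** The classification rule in Protocol 6.1.3; the classification rule and overview row in SAP 11.2.1 (both SAPs); planned arm sizes of 300 and 200 from Protocol 8.2, used only for illustration. I take the SAPs' unknown relationship to mean not reported or not assessable, since the protocol offers only two ratings.

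**Step 1: one subject, one preferred term.** Let R = Reasonable Possibility, N = No Reasonable Possibility, U = no rating. A subject's occurrences of one event can carry 2³ − 1 = 7 sets of ratings.

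| Ratings present | SAP 11.2.1 | Protocol 6.1.3 | Drug-related status differs? |
|---|---|---|---|
| R | Reasonable Possibility | associated | no |
| N | No Reasonable Possibility | not associated | no |
| U | unknown | associated | **yes** |
| R, N | Reasonable Possibility | associated | no |
| R, U | Reasonable Possibility | associated | no |
| N, U | unknown | associated | **yes** |
| R, N, U | Reasonable Possibility | associated | no |

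Two of the seven sets differ. Both move from unknown to drug-related when 6.1.3 is applied, and none moves the other way.

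**Step 2: the overview row.** This row counts subjects over all their AEs. A subject is left out relative to 6.1.3 only if at least one AE is U and none is R. Hence

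related subjects (SAP) = related subjects (6.1.3) − subjects with at least one U and no R,

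so the SAP count is less than or equal to the 6.1.3 count. The event rates per 100 patient-years that 11.2.1 plans for the overview use events as the numerator. There, each U event is omitted even when the subject also has an R event.

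**Step 3: illustrative size.** Let u be the proportion of subjects with at least one U and no R. The documents give no value for it, so the figures below are assumptions. The omitted subjects number 300u and 200u.

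| Assumed u | Higher regimen (300u) | Standard regimen (200u) |
|---|---|---|
| 0% | 0 | 0 |
| 1% | 3 | 2 |
| 2% | 6 | 4 |
| 5% | 15 | 10 |

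In percentage points the gap in each arm equals u, so 0 to 5 over this range. The Maintenance SAP gives no sample size (section 4.3), so no counts are shown for that period.

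**The case against.** The strongest defence is that the two texts do different jobs. Section 6.1.3 says how the sponsor will regard an event and sits in the chapter on adverse event assessment and reporting. The SAP outputs are labelled as the investigator's rating, and an event the investigator did not rate cannot truthfully be shown as rated 'Reasonable Possibility' by the investigator. Protocol 8.1 leaves analysis detail to the SAP, so on this view the SAP fills a gap and 'None' in section 12.1 is not plainly false. This has force against simply relabelling events, and the fix allows for it. It does not remove the point: neither document draws the distinction, and even if it is accepted, nothing planned shows the count under the sponsor's rule.

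The defence is also right that missing ratings may be rare. Protocol 6.1 requires the investigator to record relationship for each AE, and section 11.0 plans 100% source verification with discrepancy resolution.

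Three stronger readings may tempt a reader, and the documents support none of them.

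- *The events are concealed.* They appear as 'unknown' in the relationship tables, and a by-subject listing is planned. 'Unknown' also overrides 'No Reasonable Possibility', so an unrated event is never turned into an unrelated one.
- *The rule decides counts of rare serious events.* The overview rows for severe and serious events, deaths, discontinuations and special-interest events, and the special-interest categories in 11.2.2, are counted regardless of causality. Neither SAP plans a row for drug-related serious events.
- *The rule favours the higher regimen.* It applies equally to both blinded arms, and nothing in the documents suggests that ratings will be missing more often in one.

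**Conclusion.** The conflict between Protocol 6.1.3 and SAP 11.2.1 is real, is the same in both SAPs, and is not declared. Its direction is certain: the drug-related count can only equal or fall below the count under 6.1.3. Its size is not known. It is zero if no AE lacks a causality rating, and at most u per arm otherwise, with u between 0% and 5% as an assumption only. It would therefore go too far to say that drug-related AEs are under-reported in this trial; the documents show that they could be.

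The effect is confined to one overview row, its event rate, and the related category of the relationship tables. The conclusion rests on equating the SAPs' unknown relationship with unreported or not-assessable causality. It also assumes that Protocol 6.1.5 (Adverse Event Reporting), which is not in the public text used here, does not restrict the 6.1.3 rule to reporting. If it does, what remains is a need to explain the difference in the SAPs.

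**What to change.** In section 11.2.1 of both SAPs, count missing or not-assessable causality as associated in the drug-related overview row and in the maximum-relationship tables. Relabel these as 'Reasonable Possibility or causality missing/not assessable', so that the label does not attribute a rating to the investigator. Show the number of subjects and events mapped in this way, so that the investigator-rated count can be recovered.

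Alternatively, keep the investigator-rated row as it stands, add a second row under the 6.1.3 rule, and list the departure in section 12.1 of each SAP.

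Either route needs a short change to the derivation and no new data. The cost is that the stated drug-related AE figure may be slightly less favourable.

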11.2.2 Adverse Events of Special Interest

The following AEs of special interest will be summarized by number and percentage of subjects experiencing an AE of interest. The AEs of interest will be summarized and presented using primary MedDRA system organ classes (SOCs) and preferred terms (PTs) for the following AE categories:

- Any Infections AE
- Any Serious Infection AE
- Any Legionella Infection AE
- Any Diverticulitis AE
- Any Opportunistic Infection AE (Excluding Oral Candidiasis and TB)
- Any Oral Candidiasis
- Any Tuberculosis AE
- Any Active Tuberculosis
- Any Latent Tuberculosis
- Any Parasitic Infection AE
- Any Reactivation of Hepatitis B
- Any Progressive Multifocal Leukoencephalopathy (PML) AE
- Any Malignancy AE
- Any Lymphoma AE

- Any Hepatosplenic T-Cell Lymphoma AE (HSTCL)
- Any Non-Melanoma Skin Cancer (NMSC) AE
- Any Melanoma AE
- Any Leukemia AE
- Any Other Malignant AE (Excluding NMSC, Melanoma, Lymphoma, HSTCL, and Leukemia)
- Any Allergic Reaction (Including Angioedema/Anaphylaxis)
- Any Lupus-Like Reactions and Systemic Lupus Erythematosus
- Any Vasculitis AE
- Any Cutaneous Vasculitis AE
- Any Non-Cutaneous Vasculitis AE
- Any Sarcoidosis AE
- Any Autoimmune Hepatitis
- Any Myocardial Infarction Related AE
- Any Cerebrovascular Accident Related AE
- Any Congestive Heart Failure Related AE
- Any Pulmonary Embolism Related AE
- Any Interstitial Lung Disease AE
- Any Intestinal Perforation AE
- Any Pancreatitis AE
- Any Stevens-Johnson Syndrome AE
- Any Erythema Multiforme Related AE
- Any Worsening/New Onset of Psoriasis
- Any Demyelinating Disorder
- Any Amyotrophic Lateral Sclerosis AE
- Any Reversible Posterior Leukoencephalopathy Syndrome (RPLS) AE
- Any Hematologic Disorders AE (Including Pancytopenia)
- Any Liver Failure and Other Liver Event AE
- Any Humira Administration Related Medication Errors AE

- Any Injection Site Reaction AE
- Any Intestinal Stricture
- Any AE Leading to Death
- Any AE Leading to Discontinuation of Study Drug.
- Any Deaths

Additional AEs may be considered for tabulation/summary based on recommendations from Clinical and Safety as deemed appropriate.

11.3 Analysis of Laboratory Data

All laboratory data collected after first dose of maintenance study drug, or after first dose of study drug for Study M14-347 will be excluded from this analysis.

Changes from Baseline in continuous laboratory parameters will be summarized by n, mean, standard deviation, minimum value, median, and maximum value for each treatment group.

Cross (Shift) tables from Baseline to the minimum, maximum, and final value according to the normal range will be provided for each hematology, clinical chemistry parameter and urinalysis parameter except for the microscopic examination.

For selected laboratory parameter with Common Toxicity Criteria (CTC) a listing of all subjects with any laboratory determinations meeting CTC Version 3.0 of Grade ≥ 3 will be provided. For each of these subjects, the whole course of the parameter will be listed. For subjects with laboratory values with CTC ≥ 3 , all of the laboratory parameters for those subjects will be listed.

The laboratory data using Abbott platform will be used for this analysis. If the data measured using Abbott platform are not available, the Abbott equivalent (the values measured using Roche platform that were converted to Abbott equivalent) will be used.

11.3.1 Assessment of Shifts from Baseline in Liver-Specific Laboratory Variables

Baseline and post-baseline livers-specific laboratory will be categorized as follows:

- < 1.5 times the upper limit of the reference range
- ≥ 1.5 to < 3 the upper limit of the reference range
- ≥ 3 to < 5 the upper limit of the reference range
- ≥ 5 to < 8 the upper limit of the reference range
- ≥ 8 the upper limit of the reference range

For each variable, shift tables will be generated that cross tabulate the subjects' as deemed appropriate:

- Category of the baseline value versus category of the final value,
- Category of the baseline value versus maximum category

Note that the maximum category is used, rather than the category of the maximum values. The two may be different due to variation in the reference range.

No statistical tests will be performed for this analysis.

A listing of potentially clinically significant liver function laboratory values will be provided. The listing includes all subjects who met any of the following 4 criteria:

$ALT \geq 2.5 \times ULN$, or

$AST \geq 2.5 \times ULN$, or

Alkaline Phosphatase $\geq 2.5 \times ULN$, or

Total Bilirubin $\geq 1.5 \times ULN$.

